- Quality of life EQ-5D-5L

Pharmacokinetics (PK):

For 30 subjects in the study, blood samples will be taken for PK analysis on Day 1 and at 6, 12 and 24 months of treatment. The following PK parameters will be derived from the plasma concentration versus time profiles to determine the pharmacokinetics of the study drug: C_{max}, T_{max}, AUC_{0-t}, t_{1/2}, and AUC_{0-∞}. Blood samples will be drawn at the following time points: pre-infusion (baseline); 0.5 and 1 hour after the beginning of the infusion; at the end of the infusion, at 0.5±0.05, 1±0.25, 2±0.25, 4±0.25, 8±0.25, 24 ±0.5, 48±3, and 96±3) hours post-infusion and at 14±3 days post-infusion.

SAFETY ENDPOINTS:

Changes from baseline in:

- Clinical laboratory tests
- Physical examination
- Assessment of the injection site
- ECG
- Treatment-emergent adverse events
- Ability to taper off infusion pre-medication throughout the first 3 months of the study
- Requirement for use of pre-medication overall to manage infusion reactions

- Treatment-emergent anti-PRX-102 antibodies
- Treatment-emergent anti-agalsidase beta antibodies

STATISTICAL ANALYSIS:

Sample Size Rational

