8.3 Safety Variables

- Safety will be assessed by the frequency, severity, and duration of treatment-emergent AEs (adverse events), including clinically significant laboratory abnormalities, ECG changes from baseline, physical examination findings and assessment of the injection site after administration of the study drug
- Anti-Drug (i.e. PRX-102 or agalsidase beta) IgG antibodies will be assessed before dosing at: baseline, 2 and 4 weeks after the first infusion, and then every month for the first 6 months and every 3 month until the end of study through the last infusion. If a patient continues treatment in an extension study, the anti-Drug antibodies will be assessed as part of that study. For patients who end treatment with PRX-102 or agalsidase beta, anti-PRX-102 antibodies will be assessed 1 and 3 months after last infusion
- Anti-Drug IgE antibodies and tryptase will be assessed in events of hypersensitivity reaction following Sponsor request
- Ability to taper off infusion pre-medication at the start of the study
- Requirement for use of pre-medication overall to manage infusion reactions

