2.2.4 Safety Endpoints

The following safety measures will be evaluated throughout the study:

- Clinical laboratory tests
- Physical examination
- Injection site reactions
- Electrocardiogram (ECG)
- Treatment-emergent adverse events (TEAEs)
- Infusion Related Reactions (IRRs)
- Infusion pre-medication
- Treatment-emergent Anti-Drug Antibodies (ADA)
- Vital signs

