11.6 Electrocardiography (ECG)

Descriptive statistics for selected quantitative and qualitative ECG parameters will be summarized at each visit by treatment arm. For quantitative parameters, the change from baseline will be summarized. All parameters will be listed (note that for patients diagnosed with Atrial Fibrillation, all PR values are reported as 0 in the ECG report. This value should be considered as not accessible).

- 1. Quantitative ECG parameters: Mean Heart Rate
- 2. Qualitative ECG parameters: Rhythm Normal Sinus Rhythm (NSR), Conduction abnormalities, left ventricular hypertrophy, Supraventricular tachycardia, Premature atrial contraction, Atrial flutter, Atrial fibrillation, Premature ventricular contraction, Ventricular tachycardia, and any clinically abnormal findings (i.e., any abnormal condition as listed above). Note that ECG abnormalities and findings are reported as characteristic = Yes in the CRF,

except for Rhythm – Normal Sinus Rhythm (NSR), for which, an abnormality is reported as characteristic = No. For consistency purposes in the reporting, for this summary it has been reversed.

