14.3.5	Summary of Physical Examinations	Safety
14.3.6.1	Summary of Hematology Test Results	Safety
14.3.6.2	Summary of Coagulation Profile at Screening	Safety
14.3.6.3	Summary of Vitamin D at Screening	Safety
14.3.6.4	Summary of Urine Analysis Test Results	Safety
14.3.6.5	Summary of Biochemistry Test Results	Safety
14.3.7.1	Summary of Electrocardiography (ECG) Quantitative Parameters	Safety
14.3.7.2	Summary of Electrocardiography (ECG) Qualitative Parameters	Safety
14.3.8.1	Summary of Anti-Drug Antibodies	Safety
14.3.8.2	Anti-Drug Antibody Shift from Baseline	Safety
14.3.8.2a	Anti-Drug Antibody Shift from Baseline to Week 104	Safety
14.3.9.1	Summary of Concomitant Medications	Safety

14.3.9.2	Proportion of Patients who Used ACEi and/or ARB	Safety
14.3.9.3	Proportion of Patients who Used Infusion Premedication	Safety
14.3.9.4	Number of Patients with Infusion Premedication (Medication Classes) Use - Shift from Baseline	Safety
14.3.9.5	Summary of Infusion Premedication	Safety
14.3.9.6	Infusion Premedication and IRR	Safety

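### SAP 11.6 gives ECG change from baseline only for mean heart rate; no by-arm ECG shift or new-onset table is planned for rhythm, conduction and other findings

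*SAP*

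**What the plan says.** **Protocol.** The Synopsis lists ECG among its safety endpoints under the lead-in "Changes from baseline in". Treatment-emergent adverse events are a separate item in the same list. Section 8.3 describes safety as assessed through treatment-emergent adverse events, "including clinically significant laboratory abnormalities, ECG changes from baseline, physical examination findings and assessment of the injection site". The flow chart in section 9.1 schedules an ECG at screening, at baseline and at eight later visits (7, 14, 20, 27, 33, 40, 47 and 53).

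**SAP.** Section 2.2.4 lists the ECG as a safety measure without mentioning change. Section 11.6 then sets the analysis: "Descriptive statistics for selected quantitative and qualitative ECG parameters will be summarized at each visit by treatment arm". It adds "For quantitative parameters, the change from baseline will be summarized", and that class has one member: "Quantitative ECG parameters: Mean Heart Rate". The qualitative class covers sinus rhythm, conduction abnormality, left ventricular hypertrophy, supraventricular tachycardia, atrial and ventricular ectopy, flutter, atrial fibrillation, ventricular tachycardia, and a composite of any abnormality. No change, shift or new-onset summary is specified for these. PR values exist, because section 11.6 explains that they are recorded as zero in atrial fibrillation, but they are only listed.

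Section 14.1 lists two ECG tables: 14.3.7.1 for the quantitative parameter and 14.3.7.2, "Summary of Electrocardiography (ECG) Qualitative Parameters". Listing 16.2.3.6 holds the patient-level data. Under section 7.1, unscheduled procedures are only listed, and premature-withdrawal data are listed and not tabulated.

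**The concern.** Change from baseline in a yes/no finding is a within-patient quantity: who was free of it at entry and had it later. A count at each visit gives prevalence, which mixes findings present at entry with new ones. New cases can be offset by patients whose finding resolves or is intermittent. A finding that appears at different visits in different patients is never added up per patient.

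What is at stake is the reading of cardiac safety from the ECG itself. An arm could acquire new conduction or rhythm abnormalities without any planned ECG table giving the number of patients affected.

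**Working it through.** The documents give no ECG figure to reproduce, so the check has two parts: tracing where a new finding would be counted, and bounding what the by-visit counts can reveal.

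**1. Where a new ECG finding could be counted by arm**

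- *ECG tables (SAP 11.6; Tables 14.3.7.1 and 14.3.7.2).* Change for heart rate only. Findings are counted at scheduled visits. There is no within-patient count.
- *Adverse events (SAP 11.2; Tables 14.3.3.3 to 14.3.3.7).* Events starting after the first infusion are counted per patient, by system organ class and preferred term, by arm. This captures an arrhythmia or conduction finding if it is reported as an adverse event. Protocol 8.3.2.1 states that clinically significant laboratory abnormalities must be recorded as adverse events. It has no matching sentence for ECG findings.
- *Fabry clinical events (SAP 10.11; Table 14.2.14).* Atrial fibrillation, ventricular tachycardia, and pacemaker and defibrillator implantation are components counted by arm. Blinded adjudication uses adverse events and other clinical information in the database. Flutter, supraventricular tachycardia, ectopy, hypertrophy on ECG, and conduction abnormality short of device implantation are not components.
- *Mainz score (Protocol Appendix 5; SAP 10.8; Table 14.2.11.1).* The cardiovascular domain includes an ECG-abnormality item and a rating for hypertrophy on ECG, and change from baseline is analysed by domain. It is a composite with a maximum of 20, so it does not show which finding is new or in how many patients.
- *Listing 16.2.3.6.* Complete, but not summarised by arm.

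An asymptomatic conduction abnormality, for example, that is neither reported as an adverse event nor adjudicated therefore appears only in visit prevalence, the listing and, at most, the Mainz composite.

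**2. What the by-visit counts can reveal**

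Let n patients be assessed at both times, b abnormal at baseline and v abnormal at the later visit. The number newly abnormal at that visit lies between max(0, v − b) and min(v, n − b).

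The arm sizes below are the planned 52 and 26. The values of b and v are assumed, because the documents give none.

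| Arm | n | b | v | New onset at that visit | Free at baseline (n − b) | New-onset risk |
|---|---|---|---|---|---|---|
| PRX-102 | 52 | 5 | 5 | 0 to min(5, 47) = 5 | 47 | 0 to 5/47 = 10.6% |
| PRX-102 | 52 | 10 | 10 | 0 to min(10, 42) = 10 | 42 | 0 to 10/42 = 23.8% |
| Agalsidase beta | 26 | 5 | 5 | 0 to min(5, 21) = 5 | 21 | 0 to 5/21 = 23.8% |

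In the last two rows both arms show an unchanged 19.2% (10/52 and 5/26) at both times. The difference in new-onset risk could still lie anywhere from −23.8 to +23.8 percentage points.

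**3. ECGs outside the tables**

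Protocol 9.2.14 asks for the Visit 53 procedures, which include an ECG, at premature withdrawal. SAP 7.1 keeps those data out of the tables. SAP 16.2 reports 6 of 78 patients (7.7%) discontinued, so the withdrawal part affects at most those six. The documents do not give the number of unscheduled ECGs.

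**4. Comparison within the SAP**

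The SAP plans shift tables for echocardiogram findings (14.2.7), overall stress-test impression (14.2.10.2) and antibody status (14.3.8.2). Yes/no ECG findings suit the same layout.

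**The case against.** The strongest reply is that new cardiac events are already counted by arm. Adverse-event tables count them per patient, Fabry clinical events cover atrial fibrillation, ventricular tachycardia and device implantation, and the Mainz domain takes in ECG items. Section 8.3 of the protocol can also be read as placing ECG changes within treatment-emergent adverse events. The Synopsis lead-in on change is loose, since it also covers adverse events and antibodies. Protocol section 10.4 does not name ECG, and 10.4.2 specifies shift tables for laboratory values only. All eight post-baseline visits are tabulated beside baseline, with a row for any abnormality, so a net imbalance between arms would be visible. Few patients discontinued.

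Much of this stands, and it rules out several stronger readings:

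- A reader might infer that new-onset abnormalities are never counted by arm. That is wrong, because the adverse-event and Fabry-event tables count some of them.
- A reader might infer that Fabry clinical events pick up only what was reported as an adverse event. SAP 10.11 also admits other clinical information in the database.
- A reader might infer that a promised ECG shift analysis was silently withdrawn. The protocol never specified one.
- A reader might suppose that many patients have ECG abnormalities at entry. The documents give no figure, and the bounds in the check depend on b and v, which are assumed.

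What remains is that each alternative route depends on reporting, adjudication or a composite. None gives the within-patient change in each ECG finding. The Synopsis lists ECG separately from adverse events, so adverse-event counts do not clearly discharge it.

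**Conclusion.** The gap is real but limited. For a safety measure that the protocol frames as change from baseline, the SAP gives change for heart rate only and has no ECG-based shift or treatment-emergent count by arm. It affects findings that are neither reported as adverse events nor adjudicated as Fabry clinical events, such as an asymptomatic conduction abnormality, flutter or ectopy. Its numerical size cannot be taken from the documents; the 0 to 10.6% and 0 to 23.8% ranges illustrate on assumed counts what equal prevalences can conceal. The primary eGFR conclusion is untouched. The change is still worth making, because the extra table answers the protocol's question directly from data already in hand.

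**What to change.** Add to SAP 11.6, and to the list in 14.1, one by-arm table. For each qualitative parameter and for any abnormality, it should cross baseline status (absent, present, missing) with any post-baseline occurrence. State explicitly that unscheduled and premature-withdrawal ECGs count, since section 7.1 would otherwise exclude them. Report n/N new onset among patients free of the finding at baseline.

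Add PR, with change from baseline, to Table 14.3.7.1, and treat the zeros recorded in atrial fibrillation as missing. PR is the only interval that the documents mention, so the request stops there.

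The cost is one extra descriptive safety table and a few rows, programmed from data already collected and listed. No new procedures are needed.

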14.2 Figures

Number	Title	Population
15.1	Time to Discontinuation (KM)	Randomized
15.2.1.1	Mean eGFR +/-SE Over Time	ITT
15.2.1.2	eGFR Change from BL +/- SE over time	ITT
15.2.1.3	eGFR Over Time – Boxplots	ITT
15.2.1.4	eGFR Difference in Slopes – Primary and Sensitivity Analyses - Forest plot	ITT
15.2.1.5	eGFR Difference in Slopes - Subgroups - Forest Plot	ITT
15.2.2.1	Mean Plasma Lyso Gb3 +/-SE Over Time	ITT
15.2.2.2	Mean Plasma Lyso Gb3 +/-SE Over Time - Change from Baseline	ITT
15.2.2.3	Mean Plasma Lyso Gb3 +/-SE Over Time by Gender	ITT
15.2.2.4	Mean Plasma Lyso Gb3 +/-SE Over Time by Gender - Change from Baseline	ITT
15.2.3	Time to first Fabry Clinical Event (KM)	ITT

14.3 Listings

Number	Title	Population
16.2.1.1	Patient Disposition	Enrolled
16.2.1.2	Completion and Discontinuation	Randomized
16.2.1.3	Analysis Population and Reason for Exclusion	Randomized
16.2.1.4	Protocol Violations	Enrolled
16.2.1.5	Study Visits	Enrolled
16.2.1.6	Patients Demographics	Enrolled
16.2.1.7.1	Fabry Disease Medical History and Past Treatments	Enrolled
16.2.1.7.2	Fabry Disease Diagnosis and Mutations	Enrolled
16.2.1.8	Other Medical History	Enrolled
16.2.1.9	Treatment Compliance	Randomized
16.2.1.10	Compliance with Infusions and eGFR Assessments During COVID-19 Pandemic	Randomized
16.2.1.11	Dose Information (Pharmacist) (To be generated only for final analysis)	Randomized
16.2.2.1.1	eGFR	Enrolled
16.2.2.1.2	eGFR slopes and Fabry Kidney Disease Therapeutic Goals	Enrolled
16.2.2.2	Plasma Lyso-Gb3 Concentration including Change from Baseline	Enrolled
16.2.2.3	Cardiac MRI	Randomized

16.2.2.4	Echocardiogram	Randomized
16.2.2.5	Brief Pain Inventory (BPI)	Enrolled
16.2.2.6	Stress Test – Bruce Protocol	Randomized
16.2.2.7	Mainz Severity Score Index (MSSI)	Randomized
16.2.2.8	Quality of Life EQ-5D-5L	Randomized
16.2.2.9	Fabry Clinical Events	Safety
16.2.3.1	Exposure	Randomized
16.2.3.2.1	Pre-treatment Adverse Events	Randomized
16.2.3.2.2	Treatment Emergent Adverse Events	Safety
16.2.3.2.3	Treatment-Emergent Adverse Events Leading to Withdrawal or Death	Safety
16.2.3.2.4	Serious Treatment-Emergent Adverse Events	Safety
16.2.3.2.5	Related Treatment-Emergent Adverse Events	Safety
16.2.3.2.6	Infusion Related Reactions – 2H	Safety
16.2.3.2.6a	Infusion Related Reactions – 24H	Safety
16.2.3.2.7	Patients diagnosed by Covid-19	Safety
16.2.3.3	Vital Signs	Enrolled
16.2.3.4	Physical Examination	Enrolled
16.2.3.5.1	Laboratory: Anti-Drug Antibodies	Enrolled
16.2.3.5.1.1	Laboratory: Anti-Drug Antibodies: IgE	Enrolled
16.2.3.5.2	Laboratory Parameters: Hematology	Enrolled
16.2.3.5.3	Laboratory: Urine Lyso-Gb3 Concentration	Enrolled
16.2.3.5.4	Laboratory: Coagulation Profile	Enrolled
16.2.3.5.5	Laboratory: Vitamin D	Enrolled
16.2.3.5.6	Laboratory: Urinalysis (Dipstick)	Enrolled
16.2.3.5.7	Laboratory: Biochemistry, Serum Creatinine and Cystatin C	Enrolled
16.2.3.5.8	Laboratory: Spot Urine and Urinalysis (Excluding Urine Dipstick)	Enrolled
16.2.3.5.9	Laboratory: Plasma Gb3	Enrolled
16.2.3.5.10	Laboratory: Serology	Enrolled
16.2.3.5.11	Laboratories: Pregnancies	Enrolled
16.2.3.6	Electrocardiography (ECG)	Enrolled
16.2.3.7.1.1	Medications	Enrolled
16.2.3.7.1.2	Infusion Premedication	Enrolled
16.2.3.7.2	Infusion Premedication by Visit and IRR-2H	Safety
16.2.3.8	Chest X-Ray (Screening)	Enrolled
16.2.3.9	Brain MRI	Randomized
16.2.3.10	PK Concentrations	Randomized
16.2.3.11	Body Measurements	Enrolled

15. TABLES, LISTINGS AND FIGURES SHELLS

For the interim analysis this document was prepared by CROS NT.

For the final analysis this will be updated by unblinded statistician involved with discussion with FDA.

16. APPENDIX A.1 – UNBLINDED DATA ACCESS PLAN

16.1 Background

The statistical analysis plan (SAP) that was finalized on April 15th, 2021 described the planned analyses at the interim analysis (when the last patient randomized completes 12 months of treatment) and at final analysis (when the last patient randomized completes 24 months of treatment). The analyses at the interim analysis were used to support the submission of a Marketing Authorization Application (MAA) to the European Medicines Agency (EMA) with the primary analysis based on noninferiority. The SAP indicates that the final analysis will be used as a confirmatory analysis to support the re-submission for Biologics License Application (BLA) to the United States (US) Food and Drug Administration (FDA) with the primary efficacy analysis based on superiority.

Following the conversion of agalsidase beta to a full approval in March 2021, it was agreed with the FDA (End-of-Review meeting; Sep 9, 2021) that it is not necessary anymore to demonstrate superiority over agalsidase beta. Discussion with the FDA on the margin and primary analysis took place on January 21, 2022. Unblinded personnel from the Sponsor will participate in this meeting. In light of that, the Unblinded Data Access Plan is revised to reflect this change and discuss the new working model between the unblinded and blinded teams.

Since the interim analysis will be used to support a submission to EMA, a Clinical Study Report (CSR) was developed at this time, and includes treatment assignments and data listings. Since the objective of the interim analysis is to support submission, or representative of the Sponsor had to be involved, and appropriate measures were put in place to ensure confidentiality of the results and to protect the integrity of the final analysis. The CSR and other submission documents are necessarily reviewed by a selected unblinded Interim Analysis Team that will include personnel from Protalix and Chiesi and external consultants/experts. This team is responsible for creating the regulatory documents and interacting with EU regulators. This team is also involved in the interactions with the FDA, interactions that were not foreseen at the time of developing the initial statistical analysis plan. The initial plan specified that in case that such an unplanned interaction is needed, members of the unblinded Interim Analysis Team will be responsible for the content of the meeting package, participate in the meeting and have access to the minutes. To accommodate the interim analysis, it was necessary to establish a plan for maintaining the blind of all personnel directly involved in the treatment of patients in the period between the release of the interim results and the final analysis, all personnel who are involved in the assessment of the endpoints of the trial, and all personnel who will participate in the Blinded Data Review (BDR) meeting for the final data.

Firewalls were in place before the interim analysis. They are updated now due to the interactions of the unblinded team with the FDA as laid out in this document. The current document outlines the principles at a high level and each stakeholder has a more granular documentation of the processes per the role they play during the study, at the interim and final analysis. This can be either in the form of a Standard Operating Procedures (SOP) (existing or new SOPs that were constructed or was documented in other internal guidelines. As part of the confidentiality measures, all individuals with access to the unblinded data were requested to sign confidentiality forms. Each stakeholder maintains a list of the individuals who have access to unblinded data or the results, and the mechanism by which this access was granted.

Statistical programming is performed by CROS NT. The blinded statistician and statistical programmers will perform the final analysis. The unblinded statistician and statistical programmer performed the interim analysis and are part of the Interim Analysis Team.

It is important to note that regardless of the measures that were put in place, the risk for bias at the final analysis is considered low since approximately 90% of the data for the primary analyses are collected by the time of the interim analysis.

Section 16.2 describes study milestones. Section 16.3 describes the measures that are taken for the unblinded Interim Analysis Team as well as the firewalls that were put in place. Section 16.4 describes the measures that were put in place to minimize bias. Section 16.5 describes the procedures and restrictions that were put in place for the release of information at the interim analysis.

16.2 Study Milestones

Seventy-eight (78) patients were randomized into the study. The Last Patient Last Visit (LPLV) for the interim analysis was in October 2020 and for final analysis was in October 2021. The Data Base Lock (DBL) and unblinding for the interim analysis was in April 2021, and the DBL for final analysis is anticipated in the first quarter of 2022 (Table 4).

Tentative Timelines

Enrollment Complete LPLV Date DBL

Interim Analysis September 2019 October 2020 April 2021

Final Analysis N/A October 2021 Q1 2022

Table 4: BALANCE Interim and Final Analyses - Key Milestones

Out of the 78 patients randomized to the study, 6 (7.7%) patients have discontinued during the study. Data collection was completed for the majority of the patients (61%) at the time of the LPLV for the interim analysis. Table 5 presents the key milestones:

Table 5: Predicted Number of Patients per Milestone

	Interim Analysis	
	LPLV	DBL and Unblinding
Date	Oct 2020	Apr 2021
Number of patients completed 24 months of treatment or early termination	48 (61%)	60 (77)
Number of patients completed between 18-23 months of treatment	13 (17%)	13 (17%)
Number of patients completed between 12- 17 months of treatment	17 (22%)	5 (6%)
Total	78	78

Figure 1 provides a schematic of the study with key milestones and timelines for the development programs in the EU and the US, and points out the 9-12-month period (April 2021 to Q1 2022) between the two DBL, with a 6-month period between the DBL for the interim analysis and the LPLV for the final analysis.

Figure 1: Schematic of BALANCE Development Program and Study Timelines

	EU Development milestones			US Development milestones			
Oct 20, LPLV		Apr 21, DBL for		Oct 21, LPLV Final MAA	Q1 22, DBL for Final		BLA
for IA		IA					
Q4 20	Q1 21	Q2 21	Q3 21	Q4 21	Q1 22	Q2 22	Q3 22

The primary endpoint of eGFR slope is derived from serum creatinine measurements. Serum creatinine is assessed on a monthly basis, so at the time of LPLV for the interim analysis, at least 90% of the blood samples were completed and available. At the time of DBL for the interim analysis and unblinding about 96% of blood samples were taken.

The implication of these milestones is that the risk of bias for the final analysis is low and the creation of firewalls and other measures will further reduce this risk.

